14.3. Hepatic and Renal Event Adjudication

All events of potential hepatic injury, suspected liver-related clinical outcomes, and potential renal injury that occur after administration of the first dose of the investigational product will be reviewed and adjudicated by independent and blinded adjudication committees, depending on event type.

Each adjudication committee has a charter that documents the reporting of events by the study site, definition of the potential events to be adjudicated, supply of source documentation to the committee, entire data flow and process from committee membership, review of the events by the committee, reporting of the final assessment, and the working procedures of the committee.

Specific details of the events that will be adjudicated are described in the respective adjudication charters. Any changes to either the adjudication process or changes to specific events to be adjudicated will be addressed in the charters and will be communicated to all study sites outside of a protocol amendment.

The adjudication committee members will include experts with relevant adjudication experience; they will not be involved in the study as Investigators, DMC members, or consultants. Any candidate found to have a conflict or whose name is listed on the FDA debarment list will not be offered membership. Conflicts of interest are assessed regularly, and if members are found to have a new conflict of interest they will be replaced.

The adjudication of potential events will be based on available source documentation, including but not limited to individual clinical study data, hospital records, discharge summaries, and/or death certificates. The adjudication committees will not receive any individual subject treatment or site-specific information. All protected health information will remain confidential and will not be available to the adjudication committee. The assessment of events will be conducted in compliance with study-specific procedures, manuals, GCP, and all other applicable regulatory requirements, including the archiving of essential documents.

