15.3. Safety Analysis

The LTSE Population will be the primary population used for safety analyses.

Safety data, including SAEs, TEAEs, physical examinations, ECGs, vital signs, clinical laboratory assessments, and treatment discontinuations, will be assessed.

The incidence of TEAEs and SAEs will be tabulated by system organ class, preferred term, and severity.

All events of potential hepatic injury, suspected liver-related clinical outcomes, and potential renal injury that occur after administration of the first dose of the investigational product will be reviewed and adjudicated by independent adjudication committees ([Section 14.3](#)).

Laboratory parameters and vital signs will be summarized (including Hy's law) using descriptive statistics at baseline (defined as the last assessment performed before the first dose of investigational product in Study 977-311) and at each scheduled post-baseline visit in Study 977-311. The change from baseline will also be summarized. ECGs will be summarized using frequency at each visit. The shift from baseline will also be summarized.

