15.9. Data Monitoring Committee

The DMC is an independent committee that includes hepatologists, physicians, epidemiology/cardiology expert(s), and statistician(s) who will not be involved in the study as Investigators, adjudication committee members, or consultants. The independent DMC will review safety data during the conduct of the trial. In addition to the periodic review of safety data, the results of the interim analysis will also be reviewed by the DMC.

The DMC will have oversight over the study conduct as defined by the general DMC charter. All members will have considerable experience with clinical study conduct and DMCs. Any candidate found to have a conflict of interest or whose name is listed on the FDA debarment list will not be offered membership; financial disclosure will be required. Conflicts of interest will be assessed regularly, and if members are found to have a new conflict of interest they will be replaced.

The DMC will meet approximately quarterly but at least every 6 months at scheduled meetings, and ad hoc meetings will be convened, as appropriate, to review safety data. Based on review of

these data, the DMC will advise the Sponsor on the validity and scientific merit of continuing the study.

Written minutes of both the open and closed DMC sessions will be prepared. Details of this committee's responsibilities and processes can be found in the DMC charter.

Data reviewed during the meetings will include, at a minimum, disposition, demographics, exposure, clinical laboratory results, MedDRA-coded AEs, AEs leading to early withdrawal of investigational product, and hepatic adjudication results. At each meeting, detailed narratives of interval SAEs (including events resulting in death) are reviewed by the DMC, in addition to a cumulative list of all SAEs.

The DMC may agree to adjust meeting frequency based upon actual and projected safety and efficacy data availability. Adjustments to or stopping of the protocol-defined doses may be considered based on DMC evaluation of OCA safety and tolerability.

All Investigators and responsible IRBs/IECs will be informed of any decisions made by the Sponsor based on recommendations from the DMC relating to subject safety that alter the conduct of this study. The Investigators will inform the subjects of such actions, and the protocol, patient information sheet, and ICF will be revised, as appropriate.

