10.2.4.1. Pruritus

Pruritus is both the most common symptom of PBC and was the most frequently reported AE in the Phase 2 PBC studies for OCA. Accordingly, pruritus is considered an AE of special interest.

Treatment-emergent pruritus, defined as any preferred term including “Prur,” will be summarized separately by the MedDRA SOC, treatment group, and PT as a subset of all TEAEs. Summaries will include a summary of the crude incidence of Pruritus TEAEs and SAEs by system organ class and preferred terms. Hepatic Injury

Hepatic injury is defined as events included in the Hepatic Disorder Standardized MedDRA query (SMQ), excluding the following sub-SMQs: alcohol related, congenital, familial, neonatal and genetic disorders of the liver; liver infections; and pregnancy-related hepatic injury. Summaries will include a summary of the crude incidence of hepatic disorder TEAEs and SAEs by system organ class and preferred terms.

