10.2.4.3. Renal Impairment

Renal impairment is defined as events included in the following broad SMQs: acute renal failure, chronic kidney disease, proteinuria, renovascular disorders, or tubulointerstitial diseases.

Summaries will include a summary of the crude incidence of myalgia TEAEs and SAEs by system organ class and preferred terms.

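### Hepatic and renal injury are adjudicated under the protocol, but SAP section 10 defines both AESIs by SMQ terms only, specifies no summary or listing of the adjudicated results, and has no renal AESI summary as written

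*SAP*

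**What the plan says.** Protocol 15.3 (Safety Analysis) covers "All events of potential hepatic injury, suspected liver-related clinical outcomes, and potential renal injury that occur after administration of the first dose" and states that they will be "reviewed and adjudicated by independent adjudication committees". Protocol 14.3 and the Synopsis say the same and add that the committees are blinded: events are "reviewed and adjudicated by independent and blinded adjudication committees, depending on event type". Event definitions, data flow and the form of the final assessment are left to the committee charters. Protocol 15.9 gives the DMC a minimum data list that ends with "AEs leading to early withdrawal of investigational product, and hepatic adjudication results"; renal adjudication is not on it.

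SAP 10.2.4 names four AESIs: pruritus, hepatic injury, myalgia and renal impairment. The hepatic text runs on inside 10.2.4.1, under the pruritus heading: "Hepatic injury is defined as events included in the Hepatic Disorder Standardized MedDRA query (SMQ", less certain sub-queries. Its output is "Summaries will include a summary of the crude incidence of hepatic disorder TEAEs and SAEs by system organ class and preferred terms". SAP 10.2.4.3 begins "Renal impairment is defined as events included in the following broad SMQs: acute renal failure, chronic kidney disease" and goes on to proteinuria, renovascular disorders and tubulointerstitial diseases. The sentence that should specify the renal output asks for the crude incidence of myalgia events instead.

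The summaries and listings in SAP 10.2.3 are organised by coded term, severity, relationship, seriousness, withdrawal and death. None is organised by adjudicated result. The visible SAP text does not mention adjudication.

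**The concern.** Long-term safety is the primary objective, and hepatic adverse events head the OCA risk table in protocol 5.6.2. PBC is itself a progressive liver disease, so a coded liver term may reflect the disease, a laboratory fluctuation or injury on treatment. A count of terms cannot separate these. Adjudication is the step that reviews them case by case. The study has a single arm, so no control rate offsets background liver events and the classification of each event carries more weight.

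As the SAP stands, the committees' results enter no specified safety output for hepatic or renal injury. SAP section 1 requires analyses added to the planned ones to be labelled post hoc. Adjudicated tables left until the CSR of an open-label study would therefore carry that label. The renal position is worse. Version 2.0 of the protocol added renal review, yet its results appear neither in a specified SAP table nor in the DMC minimum list, and the term-based renal summary is missing as well.

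**Working it through.** No figure in the plan bears on this point. The sample size of about 133 has no statistical derivation (protocol 15.2, SAP 3.4), so there is nothing to reproduce. The check is a comparison of texts, followed by an illustration.

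**Step 1: texts side by side.**

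| Item | Hepatic injury | Renal injury |
|---|---|---|
| Sent to adjudication (protocol 14.3, 15.3) | Yes | Yes |
| Adjudicated results in DMC minimum list (protocol 15.9) | Yes | Not listed |
| AESI definition (SAP 10.2.4) | Hepatic Disorder SMQ with exclusions | Five broad SMQs |
| AESI output (SAP 10.2.4) | Crude incidence of coded TEAEs and SAEs | None; the sentence names myalgia |
| Adjudicated table or listing (SAP 10.2.3, 10.2.4) | None | None |
| Summaries that do not depend on AE reports (SAP 10.3) | Hy's law by visit; chemistry shift tables | Chemistry shift tables (creatinine and eGFR are in protocol Table 11) |

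SAP section 10 shows no blackout that could hide an adjudicated table. SAP 9.2 is partly blacked out. It plans Kaplan-Meier estimates for the components of a composite event endpoint, and MELD of at least 15 is visible there. Protocol 14.2.1 asks adjudicators to confirm that such a MELD change is sustained. Some liver outcomes may therefore be analysed as adjudicated in the exploratory part.

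**Step 2: could the two sources differ?** Let n = 133 and let r be the number of subjects with an SMQ event. Let c be the share of those confirmed by adjudication, and o the number of subjects with an adjudicated event outside the SMQ.

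- SMQ incidence = r/n
- Adjudicated incidence = (c × r + o)/n
- Exact 95% limits for k of n: lower = Beta quantile 0.025 with parameters (k, n − k + 1); upper = Beta quantile 0.975 with parameters (k + 1, n − k)

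The documents give none of r, c or o, so all three are assumptions. With r = 20, the SMQ incidence is 20/133 = 15.0% (9.4 to 22.3).

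| c | o | Adjudicated k | Incidence (95% CI) |
|---|---|---|---|
| 0.25 | 0 | 5 | 3.8% (1.2 to 8.6) |
| 0.50 | 0 | 10 | 7.5% (3.7 to 13.4) |
| 0.75 | 0 | 15 | 11.3% (6.5 to 17.9) |
| 1.00 | 0 | 20 | 15.0% (9.4 to 22.3) |
| 1.00 | 7 | 27 | 20.3% (13.8 to 28.1) |
| 0.50 | 10 | 20 | 15.0% (9.4 to 22.3) |

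With a smaller r of 7, the SMQ incidence is 5.3% (2.1 to 10.5). If 2 of the 7 are confirmed and o = 0, the adjudicated incidence is 1.5% (0.2 to 5.3).

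**Step 3: what this shows.** The ratio of the two rates only restates the assumed c and o, so it is not evidence of bias in either direction. The last row of the table matters most for the design of the output. The two rates are equal, yet 10 subjects are SMQ-positive only and 10 are adjudicated only. Two separate incidence tables would not show this; a cross-tabulation would.

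**The case against.** The strongest reply is that the SAP breaks no promise. Protocol 14.3 and 15.3 say that events will be adjudicated; they do not say that adjudicated incidence will be tabulated or will replace coded counts. Protocol 15.3.1 asks for TEAEs and SAEs by system organ class and preferred term, and SAP 10.2.3 delivers that. This stands. The gap is an omission in the SAP, and a reader who infers a direct contradiction of the protocol goes too far.

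Second, the hidden text of SAP 9.2 may contain adjudicated liver outcomes. This also stands, so the inference that the SAP analyses no adjudicated result anywhere is not supported. It does not close the gap: the visible role of 9.2 is an exploratory outcome composite, and the AESI text in section 10 is complete as shown.

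Third, hepatic and renal risk is also read from laboratory data, which do not depend on what investigators report. This stands, so it would be wrong to say that these risks are estimated from unconfirmed reports alone. The limitation is on the AESI incidences. Laboratory tables are not assessed for cause and do not cover clinical events.

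Fourth, an inclusive coded count is a defensible safety summary, and putting adjudicated rates above it would be a preference. That is accepted: nothing in the documents supports demoting the SMQ tables.

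Fifth, the DMC list is a minimum, so renal results are not excluded. True, but nothing requires them, while hepatic results are required.

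**Conclusion.** The concern holds as an omission. Protocol adjudication covers hepatic and renal injury, but SAP section 10 specifies no summary or listing of the adjudicated results. The two AESI incidences that serve the primary objective would come from coded terms only. For renal impairment even the coded summary is missing, because its output sentence names myalgia. Individual renal terms would still appear in the general TEAE tables, but no grouped renal count is specified.

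No numerical size can be attached from the documents. The illustration at N=133 rests wholly on assumed values and moves both ways: from 15.0% by SMQ to 3.8% adjudicated if a quarter of 20 subjects are confirmed, or to 20.3% if all are confirmed and 7 more lie outside the SMQ. A reader might infer that the SMQ count must overstate the risk. The documents do not support that, since the charters define what is adjudicated and were not supplied.

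The conclusion assumes that the charters yield a recorded result per event that can be tabulated. The point is worth correcting before the SAP is signed off.

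**What to change.** 1. SAP 10.2.4: add subject incidence with 95% CI, and a by-subject listing, for adjudicated hepatic injury and for adjudicated renal injury, using the categories set in the charters. Present these alongside the SMQ tables, which keep their place.
2. SAP 10.2.4: cross-tabulate SMQ status against adjudicated result in both directions, so that SMQ events not confirmed and adjudicated events outside the SMQ are both visible.
3. SAP 10.2.4.3: replace myalgia with renal impairment in the output sentence.
4. Protocol 15.9: extend the minimum DMC data from hepatic adjudication results to hepatic and renal adjudication results.

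The cost is a few extra tables and a listing from data already collected, some SAP wording and one protocol phrase. No additional subject assessment is needed.

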10.2.4.2. Myalgia

Myalgia is defined as events with the preferred term of myalgia. Summaries will include a summary of the crude incidence of myalgia TEAEs and SAEs by system organ class and preferred terms.

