5.6.3. Considerations with the Use of OCA and Bezafibrate in Combination

As both OCA and BZF are metabolized in the liver, it is important to monitor for potential hepatotoxicity through physical signs and symptoms, as well as laboratory testing of liver-related biochemical parameters. See [Section 7.4](#) for guidance on the monitoring and management of potential hepatic events and decompensation.

In considering use of BZF and OCA concomitantly and the Phase 2 study data to date, it is expected that the safety experience will be similar to the individual products. However, the overall safety profile of BZF is based on a different patient population and indication for the treatment of severe hypertriglyceridaemia and mixed hyperlipidaemia. Decreased appetite and gastrointestinal disorders were the most common undesirable effects. Per the Summary of Product Characteristics, cholelithiasis is a labeled undesirable effect of BZF (very rare) ([Bezalip Mono 2016](#), [Bezalip Mono 2020](#), [Bezafibrate Retard 2017](#), [Bezalip 2016](#), [Bezalip 2020](#)) and has also been reported in OCA clinical studies at higher doses in subjects with metabolic dysfunction-associated steatohepatitis (MASH). [Section 7.5](#) provides detailed guidelines for the medical management of subjects with symptomatic cholelithiasis and/or cholecystitis.

Treatment with drugs of the fibrate class including BZF has been associated on rare occasions with myositis or rhabdomyolysis. Myopathy should be considered in any subject with diffuse myalgias, muscle tenderness/weakness, or marked elevations in CK levels, and dose adjustment may be needed in subjects with impaired renal function. Subjects should be advised to report unexplained muscle pain, tenderness or weakness promptly, particularly if accompanied by malaise or fever. Creatine kinase (CK) levels should be assessed in subjects reporting these symptoms, and investigational product should be interrupted if markedly elevated CK levels ($\geq 5\times$ ULN or $\geq 3\times$ ULN with symptoms of rhabdomyolysis) occur or myopathy is diagnosed (Table 4). Section 7.4.4.3 provides detailed guidelines for evaluating and monitoring subjects with potential myopathy. In cases of rhabdomyolysis, administration of investigational product must be stopped immediately and renal function must be carefully monitored while rehydration is administered.

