7.4.4.3. Potential Myopathy Evaluation and Monitoring

Subjects will be monitored for potential myopathy events throughout the study. If a subject becomes aware of the development of signs and symptoms of potential myopathy (i.e., muscle weakness, muscle soreness or muscle pain), the subject will be instructed to promptly contact the site for further assessment.

Clinical criteria for the monitoring of these events and the interruption/discontinuation of investigational product is as follows:

- At Day 1/Day 2: Check baseline CK: If ≥ 5 x ULN the Medical Monitor and Sponsor Medical Monitor will determine if the subject can continue in Study 977-311 on a case-by-case basis.
- Previous History of Myalgia: Yes or No. If Yes, rate on a scale of 1 to 10 with 1 being the least amount of discomfort and 10 being the most amount of discomfort to establish baseline.
- If subjects develop symptoms of myopathy at any point during the study, CK values must be checked. A CK ≥ 5 x ULN or ≥ 3 x ULN with symptoms consistent with rhabdomyolysis will require investigational product interruption. Laboratory values including CK and creatinine will be closely monitored until values return to baseline levels (see [Table 4](#)).

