14. SAFETY ASSESSMENTS

14.1. Adverse Events and Serious Adverse Events

14.1.1. Definitions of Adverse Events

14.1.1.1. Adverse Events

AEs are defined as any untoward medical occurrence associated with the use of the investigational product in humans, whether or not considered related to the investigational product. An AE (also referred to as an adverse experience) can be any unfavorable and unintended sign (e.g., an abnormal laboratory finding), symptom, or disease temporally associated with any use of the investigational product, without any judgment about causality and irrespective of route of administration, formulation, or dose, including an overdose.

AEs include, but are not limited to, (1) a worsening or change in nature, severity, or frequency of condition(s) present at the start of the study; (2) subject deterioration due to primary illness; (3) intercurrent illness; and (4) drug interaction. For reporting purposes, pregnancy is not considered an AE but must be reported expeditiously as described in [Section 14.1.10](#).

AEs should be elicited in a general way, without leading the subject or asking about the occurrence of any specific symptom.

The Investigator should attempt to establish a diagnosis of the event based on signs, symptoms, and/or other clinical information. The diagnosis and not the individual signs/symptoms should be documented as the AE. For example, if the underlying disease process is a stroke, it would not be appropriate to record the AE by describing the symptoms “sudden numbness, dizziness, and difficulty speaking.” The AE medical term of “stroke or cerebrovascular accident” should be recorded, as it more accurately describes the AE.

Subjects should be instructed to contact the site promptly upon awareness if they develop signs and symptoms of potential hepatic decompensation such as pale-colored stools, urine color from pale to deep amber (dark), nausea, vomiting, abdominal pain, diarrhea, weight loss, fever and chills, fatigue, weakness, loss of appetite, confusion, swelling of the legs or abdomen, yellowing of the skin or whites of eyes, and bruising easily.

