10.2.3. TEAE Analyses

All AE summaries will be restricted to TEAEs. Summaries that are displayed by SOC and PT will be ordered by descending order of incidence of system organ class and preferred term within each system organ class. Summaries of the following types will be presented:

- Overall summary of TEAEs
- Subject incidence of TEAEs and the total number of entries by MedDRA SOC and PT.
- Subject incidence of TEAEs by MedDRA SOC, PT, and highest severity. At each level of subject summarization, a subject is classified according to the highest

severity if the subject reported 1 or more events. AEs with missing severity will be considered severe for this summary.

- Subject incidence of TEAEs by MedDRA SOC, PT, and closest relationship to investigational product (Related/Not Related). Related AEs are those with relationships reported as “Definite,” “Probable,” or “Possible,” and unrelated AEs are those with relationships reported as “Unlikely” or “Not Related.” At each level of subject summarization, a subject is classified according to the closest relationship if the subject reported 1 or more events. AEs with a missing relationship will be considered related for this summary.
- Subject incidence of serious TEAEs and the total number of entries by MedDRA SOC and PT.
- Subject incidence of TEAEs leading to investigational product withdrawal or study discontinuation by MedDRA SOC and PT. This is a subset of the AEs where Action Taken with Study Treatment is checked as “Drug Withdrawn” or where “Subject Discontinued from Study” is checked.

The following listings will be presented by subject:

- All adverse events
- Serious adverse events (a subset of the AEs where serious is marked as “Yes”).
- Severe adverse events (a subset of AEs where severity is marked as “Severe”).
- Related adverse events (a subset of the AEs where relationship marked as “Definite,” “Probable,” or “Possible”).
- Adverse events leading to Study Drug Withdrawal or Study Discontinuation (a subset of the AEs where Action Taken with Study Treatment is checked as “Drug Withdrawn” or where “Subject Discontinued from Study” is checked).
- Adverse events leading to death.

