10.2.4. Adverse Events of Special Interest (AESI)

The AESIs include pruritus, hepatic injury, myalgia and renal impairment.

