10.7. Prior and Concomitant Medications

Prior medications are those medications with start and stop prior to the initial dose of investigational product. Concomitant medications are those medications started prior and continued after the initial dose of investigational product were. If it cannot be determined whether the medication was a concomitant medication due to a partial start or stop date or if the medication is taken on the same date as the initial dose of investigational product, then it will be counted as a concomitant medication.

Prior medications will be listed only. Concomitant medications will be summarized by World Health Organization (WHO) Anatomical Therapeutic Chemical (ATC) class level 2, WHO ATC class level 4 and preferred name using the LTSE Population. These summaries will present the number and percentage of subjects using each medication. Subjects may have more than one medication per ATC class and preferred name. At each level of subject summarization, a subject is counted once if he/she reported one or more medications at that level. Each summary will be ordered by descending order of incidence of ATC class and preferred name within each ATC class.

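### The muscle AESI counts only the preferred term myalgia, CK is not counted at the protocol's thresholds, and two neighbouring SAP sentences (renal AESI, concomitant drugs) need correcting

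*SAP*

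**What the plan says.** **AESI list.** SAP 10.2.4: "The AESIs include pruritus, hepatic injury, myalgia and renal impairment".

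**Muscle.** SAP 10.2.4.2: "Myalgia is defined as events with the preferred term of myalgia". It gives no term group and no CK criterion.

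**The muscle risk in the protocol.** Protocol 5.6.3: "Treatment with drugs of the fibrate class including BZF has been associated on rare occasions with myositis or rhabdomyolysis". The same section and Table 4 treat CK of at least 5x ULN, or at least 3x ULN with rhabdomyolysis symptoms, as the marked-elevation criteria. Protocol 7.4.4.3 adds: "Subjects will be monitored for potential myopathy events throughout the study".

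**How events are recorded.** Protocol 14.1.1.1: "The diagnosis and not the individual signs/symptoms should be documented as the AE". Protocol 14.2.6 has clinically significant laboratory changes recorded as AEs when no documented AE accounts for them.

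**CK output.** SAP 10.3 gives sex- and age-specific CK ranges, descriptive statistics, and shift tables in three categories (low, normal, high). SAP 5.5 restricts analyses to scheduled visits and leaves unscheduled ones to listings.

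**Renal.** SAP 10.2.4.3 defines renal impairment by five broad SMQs, then states: "Summaries will include a summary of the crude incidence of myalgia TEAEs and SAEs by system organ class and preferred terms".

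**Medications.** SAP 10.7 defines prior drugs as those both started and stopped before first dose, and these are listed only. For the drugs that are tabulated it says: "Concomitant medications are those medications started prior and continued after the initial dose of investigational product were". A fallback counts a drug as concomitant if a partial date leaves its status undeterminable or if it was taken on the first-dose date.

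**The concern.** Long-term safety is the primary objective, and there is no control arm. The AESI tables are the prespecified place to see the risks particular to this combination. A muscle AESI limited to one symptom term works against the recording rule: once muscle pain is diagnosed as myositis or rhabdomyolysis, the diagnosis is what gets recorded, and the event leaves the AESI count. The more serious the diagnosis, the less likely the AESI summary is to show it.

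The SAP treats its other AESIs more broadly. Hepatic and renal events use SMQs, and pruritus uses any preferred term containing a given text string. Only muscle rests on one term.

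The other two faults affect tables a reader would use to interpret muscle and renal events. As written, the renal AESI has no correctly specified summary. The medication table omits drugs newly started during up to 60 months of follow-up, although SAP 9.1 names prohibited-medication use as an intercurrent event and Protocol 9.2.1 disallows statins.

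**Working it through.** The plan states no figure on this point, so the check sets the definitions side by side.

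**Step 1. Which muscle events reach which output**

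| Event as recorded | Muscle AESI (SAP 10.2.4.2) | General TEAE tables (SAP 10.2.3) |
|---|---|---|
| Myalgia | Counted | Counted |
| Myositis | Not counted | Counted |
| Rhabdomyolysis | Not counted | Counted |
| Myopathy | Not counted | Counted |
| Muscular weakness | Not counted | Counted |
| CK increased | Not counted | Counted |

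The last column follows from SAP 10.2.3: "Subject incidence of TEAEs and the total number of entries by MedDRA SOC and PT". Serious cases also enter the serious TEAE table.

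**Step 2. Whether the CK laboratory output fills the gap**

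Multiplying the upper limits in SAP 10.3 by 3 and by 5:

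| Group | ULN (U/L) | 3x ULN | 5x ULN |
|---|---|---|---|
| Female, 18-80 | 182 | 546 | 910 |
| Male, 18-50 | 439 | 1317 | 2195 |
| Male, 51-80 | 331 | 993 | 1655 |

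A woman with CK of 183 U/L and one with 910 U/L fall in the same high cell of the shift table, although the second is at the protocol's 5x level. The shift to worst value does not separate them either.

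Timing adds to this. Protocol Table 3 schedules CK at Months 1, 3, 6 and 12 and then every 6 months to Month 60. That is 4 + (60 − 12)/6 = 4 + 8 = 12 scheduled post-baseline results for a subject who completes. Symptom-triggered CK (Protocol 7.4.2 and 7.4.4.3) will often come from unscheduled visits, and under SAP 5.5 those results go to listings only.

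**Step 3. Renal**

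The SMQ definition in 10.2.4.3 is complete. The sentence after it repeats the one in 10.2.4.2 and names myalgia. Read literally, the defined renal events are never tabulated as an AESI.

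**Step 4. Medication classes under the wording of SAP 10.7**

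| Timing of drug | Class | Output |
|---|---|---|
| Started and stopped before first dose | Prior | Listed |
| Started before, continued after first dose | Concomitant | Tabulated |
| Taken on the first-dose date | Concomitant | Tabulated |
| Undeterminable because of a partial date | Concomitant | Tabulated |
| Complete start date after the first-dose day | Neither | Listed (SAP 5), not tabulated |

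First dose is at the Day 2 visit (Day 2 to Day 7), so a drug begun between Day 1 and first dose and then continued is tabulated. The gap begins the day after first dose. Protocol 9.2 requires drugs taken during the study to be entered in the eCRF, so the data exist.

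**Step 5. Scale**

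Neither document gives a rate of serious muscle events on the FDC tablet. One subject in the planned 133 is 1/133 = 0.75%. That is the change in the AESI percentage for each subject whose only muscle event carries an uncounted term. It is a unit of scale and not a forecast.

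**The case against.** The strongest reply is that little is hidden. SAP 10.2.3 tabulates every TEAE by SOC and preferred term, by severity and by relationship, with separate tables for serious events and for events leading to withdrawal. Protocol 14.3 sends potential renal injury to independent adjudication, and Protocol 15.9 gives the DMC narratives of interval SAEs. CK has ranges, summaries, shifts and listings. This stands. A reader might infer that serious muscle and renal events disappear from reporting; the documents do not support that. The gap is in the AESI summary and the CK threshold counts. The adjudication described in Protocol 14.3 covers hepatic and renal events, however, and does not mention muscle events.

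Second, the SAP calls the AESI myalgia and defines it consistently, and Protocol 5.4.2 reports arthralgia and myalgia as the most frequent AEs in the cited bezafibrate trial. So this is a choice and not an internal contradiction. That is true, but it is a poor match to the risks the protocol singles out.

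Third, the renal sentence is an obvious slip, since the heading, the AESI list and the SMQs all show the intent. This also stands.

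Fourth, the sentence in SAP 10.7 is visibly broken, and words may be missing. A reader might infer a deliberate rule to leave out all drugs started on study. The text does not support that: the omission is probably unintended, and it applies to complete start dates after the day of first dose. Prohibited drugs might also surface under major protocol deviations (SAP 6.1), if classed as major. Because that intercurrent event is handled by treatment policy, no efficacy estimate depends on this table.

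**Conclusion.** The point holds as a defect in prespecified summaries. It is worth correcting before the SAP is finalised, and it does not threaten the underlying safety data.

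- **Muscle AESI and CK:** this is the substantive part. The AESI summary would omit the named fibrate diagnoses, and no planned table counts subjects at the protocol's own CK levels.
- **Renal AESI:** an apparent copy error with clear intent.
- **Concomitant drugs:** a garbled definition that, as worded, leaves drugs started after the day of first dose out of the table but in the listings.

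The conclusion assumes that sites follow the diagnosis-recording rule, that programming follows the SAP text literally, and that SAP 5.5 governs the CK tables. It does not rest on any assumed event rate. A reader might try to size the point by comparing confidence limits for one case against none. That would describe a hypothetical case, and the SAP plans crude incidence without inferential safety comparisons, so the comparison should not be used.

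**What to change.** 1. **SAP 10.2.4.2.** Define the muscle AESI by a prespecified grouped term list or SMQ covering rhabdomyolysis, myopathy, myositis, muscular weakness and CK increased, plus the preferred term myalgia. Show myalgia as its own row so that the symptom count is kept.
2. **SAP 10.3.** Add the number and percentage of subjects with CK of at least 3x ULN and at least 5x ULN at any result after first dose, including unscheduled visits, as a stated exception to SAP 5.5. Say which ULN applies to local-laboratory results.
3. **SAP 10.2.4.3.** In the summary sentence, replace myalgia with renal impairment.
4. **SAP 10.7.** Define concomitant medication as any drug taken on or after the first FDC dose in Study 977-311, whatever its start date, and flag prohibited drugs.

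The cost is SAP wording and a little programming, with no new data collection and no change to subject management. The broader muscle group will bring in some non-specific events. Making the change now also matters for labelling: under SAP 1, analyses added later to supplement the plan must be identified as post hoc in the CSR.
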